
DOSE/ROUTE/REGIMEN (TEST ARTICLE AND REFERENCE TREATMENT):
 
A dose adjustment will be made for patients whose body weight is ≤ 50 kg at screening; these patients will receive one-half the otherwise specified doses of study medication (weight will be measured at each visit and the dose increased at the Investigator’s discretion if the patient’s weight reaches > 50 kg).
 
Double-blind Period
 
The full daily dose for both sparsentan (active) and irbesartan (control) will preferably be taken prior to the morning meal, with the exception of the day of a study visit. On the day of a study visit, the patient will take their study medication at the clinic. At the visits specified in Section 15.1, study medication will be administered at the clinic after the pre-dose pharmacokinetic (PK) blood sample has been obtained. Allowed doses during the double-blind period are shown in Table 2.
 
Patients will receive the initial dose (ie, one-half the target dose) based on screening body weight for the first 2 weeks. The Investigator will evaluate dose tolerance in a blinded manner prior to titrating up to the target dose; tolerance is defined as blood pressure measurements $> 100/60$ mmHg (patients ≥ 18 years of age) or above the 5th percentile for sex and height (patients < 18 years of age; Banker 2016) after 2 weeks and no adverse events (AEs) or laboratory findings interfering with the patient’s continuation on study medication. Patients who display asymptomatic blood pressure values $\leq 100/60$ mmHg (patients ≥ 18 years of age) or $\leq 90/50$ mmHg or are below the 5th percentile for sex and height (whichever is lower in patients < 18 years of age) or who present with clinical symptoms of orthostatic hypotension but otherwise tolerate the initial dose will continue after the Week 2 visit without titrating up to the target dose (see Section 8.1 and Section 8.3.2).
 
At the Investigator’s discretion, patients weighing > 50 kg who do not tolerate the initial dose for any reason (including changes in laboratory parameters assessed at Week 2) may continue at one-half the initial dose. Patients weighing ≤ 50 kg who do not tolerate the initial dose for any reason (including changes in laboratory parameters assessed at Week 2) will be discontinued from the study.
 
Open-label Extension
 
The full daily dose will preferably be taken prior to the morning meal. Allowed doses during the open-label extension are shown in Table 3.
 
Patients who are taking 2 capsules of study medication (ie, 400 mg sparsentan or 150 mg irbesartan) at the end of the double-blind period will initiate treatment in the open-label extension at 200 mg sparsentan for the first 2 weeks of the open-label extension. Likewise, patients who are taking 4 capsules of study medication (ie, 800 mg sparsentan or 300 mg irbesartan) at the end of the double-blind period will initiate treatment in the open-label extension at 400 mg sparsentan for the first 2 weeks of the open-label extension. Following 2 weeks
	

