6.3. Patient Completion and Overall Study Completion

6.3.1. Patient Completion of the Double-Blind Period

Each patient will participate in the double-blind period of the study for approximately 6 weeks during the screening phase, followed by 108 weeks of double-blind treatment. At the end of the 108-week treatment period, study medication will be discontinued and replaced with standard-of-care therapy treatment, including treatment with RAAS inhibitors provided there are no contraindications for their use. If the patient was treated with irbesartan at study entry, an alternative ARB at an equivalent dose is required from Week 108 to Week 112. The Investigator may make additional adjustments in antihypertensive medications as necessary to adequately control the patient's blood pressure.

Patients will return to the site for the final (Week 112) visit 4 weeks later. Thus, patients will participate in the double-blind period for a total of approximately 118 weeks or about 30 months.

A patient will be considered as having completed the double-blind period, regardless of whether the patient is on or off study medication, if the patient is followed until Week 112. The need for additional intervention for the treatment of FSGS or the occurrence of safety endpoints do not constitute completion of the double-blind period and are not criteria for withdrawal from the study or study medication.

Patients who successfully complete the final Week 112 Visit will complete the assessments listed in the schedule of events ([Section 15.1](#)). Patients who received blinded study medication throughout the duration of the double-blind period (ie, did not permanently discontinue study medication) may be eligible to enroll in the open-label extension (see [Section 7.2](#)).

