6.4.2. Permanent Discontinuation of Study Medication

During the course of this long-term study, it is anticipated that patients may permanently discontinue study medication (sparsentan or irbesartan) for any of the following reasons:

- Receipt of kidney transplant or initiation of RRT
- Any SAE, AE of interest (AEOI; see [Section 10.3](#)), clinically significant laboratory abnormality, intercurrent illness, or other medical condition that indicates to the Investigator that continuation on study medication is not in the best interest of the patient
- Significant protocol deviation (ie, patient failed to meet entry criteria or did not comply with protocol requirements resulting in an unacceptable risk to the patient's health)
- Investigator discretion
- Patient (or parent/legal guardian) decision to stop study medication
- Patient pregnancy
- Diagnosis of Class II-IV CHF
- Hyperkalemia resistant to treatment (see Appendix B, [Section 15.2.2](#) for hyperkalemia management guidelines)
- Termination of the study by the Sponsor, US Food and Drug Administration (FDA), or other regulatory authorities (see [Section 13.4.5](#))
- Lost to follow-up

Therapy to treat relapse (that is a new or substantial change in immunosuppression) during the study is not a reason for permanent study medication discontinuation.

Patients who permanently discontinue study medication during the double-blind period should be encouraged to continue study visits through Week 112 for continued collection of safety and efficacy data despite stopping study medication, but may withdraw consent at any time (see [Section 6.5](#)). Patients who agree to continue regularly scheduled study visits will complete the End of Treatment (EOT) assessments listed in the schedule of events ([Section 15.1](#)) as close as possible to the patient's last dose of study medication. The visit data, including the primary reason for discontinuation of study medication, will be recorded on the EOT electronic case report form (eCRF). Subsequent study visit data will be recorded on the visit-specific eCRF, and the patient's final study visit will be recorded on the End of Study (EOS) eCRF.

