6.5. Discontinuation of the Patient from the Study

Patients are free to withdraw consent and/or discontinue participation in the study at any time without prejudice to subsequent standard-of-care treatment. A patient's participation in the study may also be discontinued at any time at the discretion of the Investigator or Sponsor. Patients may also be discontinued from the study if the study is terminated (see [Section 13.4.5](#)).

Patients may be permanently discontinued from the study for any of the following reasons:

- Death
- Voluntary withdrawal of patient/guardian assent/consent (complete withdrawal of consent requires a patient's/parent's/guardian's refusal of ALL methods of follow-up noted in the informed consent form [ICF])
- Termination of the study by the Sponsor, US FDA, or other regulatory authorities (see [Section 13.4.5](#))
- Lost to follow-up

In general, patients should be encouraged to remain in the study until they complete the double-blind period. A patient who permanently discontinues from the study during the double-blind period will complete the early termination (ET) assessments listed in the schedule of events ([Section 15.1](#)) as close as possible to the patient's last dose of study medication. The visit data, including the primary reason for premature discontinuation from the study, will be recorded on the EOS eCRF.

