titrating up to the target dose; tolerance is defined as blood pressure measurements >100/60 mmHg (patients ≥18 years of age) or above the 5th percentile for sex and height (patients <18 years of age; [Banker 2016](#)) after 2 weeks and no adverse events (AEs) or laboratory findings interfering with the patient’s continuation on study medication. Patients who display asymptomatic blood pressure values ≤100/60 mmHg (patients ≥18 years of age) or ≤90/50 mmHg or below the 5th percentile for sex and height (whichever is lower in patients <18 years of age), or who present with clinical symptoms of orthostatic hypotension but otherwise tolerate the initial dose will continue after the Week 2 visit without titrating up to the target dose. At the Investigator’s discretion and in consultation with the Medical Monitor, patients weighing >50 kg who do not tolerate the initial dose for any reason (including changes in laboratory parameters assessed at Week 2) may continue at one-half the initial dose. Patients weighing ≤50 kg who do not tolerate the initial dose for any reason (including changes in laboratory parameters assessed at Week 2) will be discontinued from the study.

The Week 2 PK sample will be drawn prior to escalating the patient to the target dose.

Dose modification is permitted as presented in [Section 8.3.2](#).

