8.3.2. Dose Modification, Reduction, or Discontinuation

Patients who display asymptomatic blood pressure values $\leq 100/60$ mmHg (patients ≥ 18 years of age) or $\leq 90/50$ mmHg or are below the 5th percentile for sex and height (whichever is lower in patients < 18 years of age), or who present with clinical symptoms of orthostatic hypotension (see [Section 9.6](#)) but otherwise tolerate the initial dose will continue after the Week 2 visit (or the Week 114 visit for the open-label extension) without titrating up to the target dose. Patients who do not titrate up to the target dose at Week 2 (or Week 114) may titrate up to that dose at any time, based on evaluation of the Investigator, in consultation with the Medical Monitor as needed. Reductions from the target dose back to the initial dose are permitted at any time after titrating up to the target dose.

Patients weighing > 50 kg at screening who do not tolerate the initial dose for any reason may continue at one-half the initial dose at the Investigator's discretion and in consultation with the Medical Monitor, as needed. Patients weighing ≤ 50 kg at screening who do not tolerate the initial dose for any reason will be discontinued from the study.

In patients with temporary dose interruptions, treatment should be resumed whenever possible (including between visits), and treatment resumption should be considered at every visit following study medication interruption.

Doses may be modified at any time throughout the open-label extension for safety/tolerability reasons at the Investigator's discretion. In addition, after titration to the target dose for the open-label extension, increases above the target doses of 200 mg or 400 mg sparsentan may be considered for patients who, in the Investigator's opinion (and following consultation with the Medical Monitor), would benefit from an increased dose.

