10.7. Reporting Adverse Events and Serious Adverse Events

10.7.1. Reporting Adverse Events

Adverse events (including SAEs) will be captured from the time informed consent is signed to the patient's final visit.

For patients who prematurely discontinue study treatment (see [Section 8.3.2](#)) but who are not withdrawn from the study, AEs will continue to be recorded until the patient completes the study (see [Section 6.3.1](#) for definition of patient completion).

If a patient initiates RRT after premature discontinuation of study treatment, only AEs and SAEs considered related or possibly related to study treatment need to be recorded.

Adverse events will be recorded using appropriate medical terminology. When recording, it is preferable to provide a diagnosis. In the absence of a diagnosis, each sign and symptom will be captured as a unique AE. Sufficient information should be sought to assist the Investigator both in determining the diagnosis and in making a causality assessment.

Reporting should not be delayed pending receipt of all required information. If information is unavailable at the time of the initial report, the Investigator is expected to follow-up until the required information has been obtained.

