10. SAFETY AND TOLERABILITY

Safety analyses will be conducted using the Safety Analysis Set at both interim and final analysis. At the interim analysis, all available data will be summarized. Unless otherwise noted, all safety analyses will be conducted using on-study data. All safety analyses specified below refer to the double-blind period only, except where noted. If >5% of patients initiate RRT while on study, select summaries excluding results after initiation of RRT may be prepared.

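### Patients of 50 kg or less who cannot tolerate the initial dose must leave the study, although the protocol elsewhere separates stopping drug from leaving follow-up

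*Protocol*

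**What the plan says.** The rule appears three times in the protocol, each time for patients of 50 kg or less who do not tolerate the initial dose:

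- Section 8.3.2: such patients "who do not tolerate the initial dose for any reason will be discontinued from the study".
- Synopsis, Dose/Route/Regimen: the rule extends to Week 2 laboratory changes, "including changes in laboratory parameters assessed at Week 2) will be discontinued from the study".
- Section 8.1.1: the same consequence, "will be discontinued from the study".

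The sections on completion and discontinuation read differently:

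- Section 6.3.1: "A patient will be considered as having completed the double-blind period, regardless of whether the patient is on or off study medication", provided follow-up reaches Week 112.
- Section 6.4.2: adverse events, clinically significant laboratory abnormalities and investigator discretion are reasons to stop drug. Patients who stop "should be encouraged to continue study visits through Week 112 for continued collection of safety and efficacy data despite stopping study medication".
- Section 6.5: "Patients may be permanently discontinued from the study for any of the following reasons". The reasons are death, withdrawal of consent, study termination and loss to follow-up. Dose intolerance is not among them, although a separate sentence allows removal at the investigator's or sponsor's discretion.
- Section 10.7.1 cites 8.3.2 as the section on stopping treatment early. For patients who do so "but who are not withdrawn from the study, AEs will continue to be recorded until the patient completes the study".

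**The concern.** A Week 2 laboratory abnormality in a 45 kg patient can fall under both Section 6.4.2 (stop drug, encourage continued visits) and Section 8.1.1 (leave the study). Table 2 of the protocol allows no dose below the initial one for patients of 20 to 50 kg. That explains why drug has to stop, but it does not explain why observation should end.

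The patients removed have been randomized and dosed, so they remain in the Full Analysis Set and the Safety Analysis Set. They have also already shown intolerance, so ending their observation early weakens the safety record in the patients where it matters most. If tolerability differs between arms, the loss will differ too, and the documents give no basis for assuming that it does not.

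**Working it through.** No power or sample size figure is involved. The check compares the text, traces which analyses are touched, and counts what is lost per patient.

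**1. Is removal mandatory?** Yes, as written. The three dosing statements say that it will happen, and 8.3.2 applies it whatever the reason for intolerance. Section 6.4 asks investigators to discuss staying in the study whenever drug is about to be stopped, with no exception by weight. Section 10.3.1 lets a patient whose liver enzymes rise again on re-introduction stay in the trial off drug. Intolerance at 50 kg or less is the exception to this pattern, and no reason is given for it.

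**2. Which analyses are untouched?**

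- Both primary slopes (SAP 8.5.1.1, 8.5.1.2) and the Week 6 to 108 MMRM (SAP 8.7.1) use on-treatment eGFR, which SAP 8.1 limits to 3 days after the last dose.
- Both Week 112 ANCOVAs (SAP 8.7.2, 8.7.3) include only patients who completed 108 weeks of treatment.

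**3. Which analyses lose data?**

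- *Safety.* SAP 10 states: "Unless otherwise noted, all safety analyses will be conducted using on-study data". Protocol 10.7.1 collects adverse events up to the final visit. Early termination assessments (6.5), suspected-related later SAEs (10.7.2) and follow-up of ongoing SAEs (10.7.3) remain covered. New non-serious events, and new SAEs not suspected to be related, are not.
- *Exploratory composites of 40% or 30% eGFR reduction, ESRD or death (SAP 8.8.4).* Renal replacement therapy and death after exit may go unascertained. SAP 6.6.2.1 counts a patient without the required assessment as a nonresponder. Read literally for these composites, a removed patient counts as event-free.
- *Robustness analysis at 4 weeks after end of treatment (SAP 8.7.2, 8.7.3).* SAP Table 2 needs an eGFR 14 to 84 days after the last dose. The early termination visit is held as close as possible to the last dose.

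**4. Size per affected patient, assuming last dose at the Week 2 target day (Day 15).**

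- Scheduled post-baseline double-blind visits (Protocol Table 1): Weeks 2, 4, 6, 8, 12, 24, 36, 48, 60, 72, 84, 96, 108 and 112, which is 14. After Week 2: 14 − 1 = 13.
- Observation lost: 112 − 2 = 110 weeks.
- Post-treatment window: Day 15 + 14 = Day 29 to Day 15 + 84 = Day 99. Target: Day 15 + 28 = Day 43, which is the Week 6 target day.
- Target days inside that window: Week 4 (29), Week 6 (43), Week 8 (57) and Week 12 (85). None of these visits would take place, and an early termination visit near Day 15 falls before the window opens.

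**5. Number of patients.** The documents do not give it. As an illustration on assumed inputs only: if 5% to 15% of 300 patients weigh 50 kg or less and 5% to 10% of those are intolerant, the range is 300 × 0.05 × 0.05 = 0.75 to 300 × 0.15 × 0.10 = 4.5, or about 1 to 5 patients.

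**The case against.** The case for leaving the text alone has four parts.

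*The conflict is softer than it looks.* Sections 6.4.2 and 6.5 encourage follow-up and do not require it, patients may withdraw consent, and Section 6.5 allows discretionary removal. This is accurate. But a discretion to remove an individual is not a rule removing a weight group, and under 8.3.2 a willing patient has no choice.

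*The text may simply mean stopping drug.* The cross-reference in 10.7.1 supports that reading, and it is the likely intent. If sites read it so, the losses do not occur. The literal instruction still says otherwise in three places, and sites act on it.

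*The trigger is narrow.* Under 8.1.1 and 8.3.2, asymptomatic low blood pressure or orthostatic symptoms in a patient who otherwise tolerates the dose lead to staying on the initial dose, and temporary interruption is also available. This stands and is a reason to expect few cases.

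*The consequences are peripheral.* The composites are exploratory. SAP 8.8.4 uses the last value on randomized treatment to confirm eGFR decline and does not say whether renal replacement therapy or death after stopping counts. Entry requires a screening eGFR of at least 30. An eGFR near Week 6, after two weeks at the initial dose, says little about a two-year effect. Much of the lost time is off drug, and the selected on-treatment summaries count events only to 30 days after last dose (SAP 10.1.3). All of this stands and limits the importance. It does not dispose of the safety point: an early termination visit close to the last dose does not cover even that 30-day window.

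The per-patient figures also assume exit at Week 2 and full attendance otherwise. Intolerance can arise later, and the loss is then smaller.

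**Conclusion.** The concern holds. Three protocol statements make study exit mandatory for a group defined by weight, against the protocol's own separation of stopping drug from leaving follow-up. The confirmatory analyses are not affected. The loss falls on safety reporting, the exploratory renal composites and one robustness analysis, and at its largest it is nearly the whole double-blind follow-up of each affected patient. Confidence is high for the conflict in wording. How much data is actually lost depends on how sites read the rule, how many patients meet it and how many would have agreed to stay. The documents give none of these, nor any split by arm.

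**What to change.** In the synopsis, Section 8.1.1 and Section 8.3.2, state that patients of 50 kg or less who do not tolerate the initial dose permanently stop study medication and are followed as described in Section 6.4.2. Dosing, blinding, sample size and the primary analysis stay as they are. The cost is an amendment to one phrase in three places, plus the scheduled visits that these patients agree to attend.

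If any patient has already left the study under the current wording, the study report should give the number by arm, the timing of exit, and how these patients were handled in the safety summaries and the composite endpoints.

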8.4. Prior and Concomitant Medications and Therapeutic Procedures

For enrolled patients, concomitant medications and concomitant therapies will be collected from the 3 months prior to screening through the patient's final study visit. In addition, a lifetime history of medications previously used for treatment of FSGS, including systemic corticosteroids or other systemic immunotherapeutic agents, will be collected. Prohibited concomitant medications and other concomitant medication considerations during study participation are outlined in [Section 15.2.1](#).

8.5. Method of Assigning Patients to Treatment (Randomization)

This study will be conducted in a double-blind, active-controlled manner. Enrolled patients will be randomly assigned in a 1:1 ratio to sparsentan or the active control (irbesartan) based on a predefined randomization code (generated by the Sponsor or designee) via the IWRS at the Day 1/Randomization visit. Randomization will include stratification by screening eGFR and UP/C values. The strata will be as follow:

- eGFR strata:
 - ≥ 30 to < 60 mL/min/1.73 m² (all patients)
 - ≥ 60 mL/min/1.73 m² (all patients)
- UP/C strata:
 - ≤ 3.5 g/g (396 mg/mmol; patients ≥ 18 years of age) or ≤ 2 g/g (226 mg/mmol; patients < 18 years of age)
 - > 3.5 g/g (396 mg/mmol; patients ≥ 18 years of age) or > 2 g/g (226 mg/mmol; patients < 18 years of age)

8.6. Blinding and Emergency Unblinding

The patient's treatment allocation will remain blinded to all parties involved with the study throughout its course (including during the open-label extension), with the exception of the Data Monitoring Committee (DMC; see [Section 13.2](#)), study medication supply, the SAE reporting contact, and the independent statistical team responsible for the interim analysis (see [Section 12.11](#)). Double-blind treatment will not be unblinded for initiation of open-label treatment. The randomization schedule for treatment allocation will be securely maintained and will not be disclosed until after database lock for the entire study.

Doses allowed during the study are shown in [Table 2](#) and [Table 3](#), and dose modifications are discussed in [Section 8.3.2](#).

For emergency unblinding only, randomization codes and corresponding treatment assignments will be made available to the Investigator through the IWRS system. When possible, the Medical Monitor should be consulted if a medical emergency necessitates unblinding (ie, in situations where knowledge of the unblinded treatment is necessary for further medical management of the patient). If it is not reasonable to inform the Medical Monitor in advance of unblinding, the Investigator must promptly document the case in the patient's study record. Subsequently, the Investigator should contact the Medical Monitor to explain any premature unblinding of treatment assignment (eg, accidental unblinding or unblinding due to an SAE). Procedures for unblinding a patient's treatment will be provided separately to the Investigator. Similarly, if the Medical Monitor breaks the blind to evaluate an emergent safety issue or for regulatory reporting purposes, the Medical Monitor will document within study correspondence the rationale, circumstances, and the person(s) being informed about the unblinding.

Access to randomization codes and corresponding treatment assignments will be made available through the IWRS system to the appropriate, named individual(s) responsible for unblinding suspected, unexpected serious adverse reactions (SUSARs) for reporting to regulatory authorities.

